RESEARCH PROTOCOL

The “*What is a Protocol?*” file on the HREB ethics website requested that applicants provide information about both the scientific and ethical aspects of their proposal. We will therefore divide this protocol description into those two sections.

1. Scientific Elements

(a) Background Research

In 2010 - 2011, more than 762,000 total knee arthroplasty (TKA) surgical procedures were performed across Canada (1). This number is expected to increase dramatically in the coming years with the growing older adult population and with the recently quantified TKA projections for younger patients (2). The growth of this procedure has resulted in increasing reports of dissatisfaction and poor outcomes such as increased pain, unmet expectations, reduced daily functioning (3), and compromised psychological health (4). Although suboptimal outcomes are not unusual in surgical procedures, there is a discrepancy in the proportion of poor outcomes associated with TKA compared to other arthroplasties. For example, 18-20% of patients following TKA report dissatisfaction (3, 5) compared to only 7% following a total hip arthroplasty (6). In response to these discrepant findings, there have been a significant number of studies that have identified psychological and psychosocial factors that are implicated in poor outcomes of TKA, even when controlling for medical factors such as surgical technique (7). This is not surprising given that more than 50% of adults undergoing TKA suffer from osteoarthritis, which has high comorbidity rates with mental disorders (8). Although psychological factors have been identified as contributing to poor outcomes, it is not clear whether an evidence-based psychological intervention can positively impact post-TKA sequelae. This study aims to pilot the effectiveness of an empirically supported intervention, mindfulness based stress reduction (MBSR), on post-TKA outcomes using a superiority randomized controlled trial (RCT) design.

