Preliminary Surgical-Related Outcomes. Despite this compelling evidence, there is little research examining MBSR in surgical contexts. One preliminary study investigating MBSR postoperatively following a spontaneous subarachnoid hemorrhage surgery found it resulted in significant decreases in ratings of depression and physical

stress, suggesting it was successful in both reducing psychological symptoms and improving homeostasis control mechanisms of the autonomic nervous system (37).

(b) General Overview of the Research Plan

The current research will consist of a pre-surgical MBSR course compared to a treatment-as-usual condition to evaluate post-surgical outcomes, including post-operative pain (severity and catastrophizing), improved physical functioning (interference and illness impact), post-surgery complications, and psychological factors including enhanced quality of life, reduced emotional distress (anxiety and depressive), enhanced cognitive skills, and improved sleep. The data will reveal if MBSR is feasible in a TKA population and determine if there are post-surgical benefits, as compared to the treatment as usual (TAU) group.

(c) Objectives, Research Design, and Hypotheses

Objective: The primary objectives are (a) to determine if an 8-week pre-operative MBSR program is feasible in a TKA population, and (b) to determine if this program results in reductions in post-operative pain (pain behavior, pain catastrophizing), improved physical functioning (pain interference, psychosocial illness impact), enhanced quality of life (global health), reduced emotional distress (anxiety and depression), enhanced cognitive skills (Cognitive Concerns), and improved sleep (fatigue, sleep disturbance) compared to TAU.

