Research Design: Forty-five participants on the waitlist for a TKA will be recruited from Concordia Hospital Hip and Knee Institute – a facility that performs 800 TKA's per year. Participants will be divided into two groups: the MBSR group prior to surgery (30 participants, divided into two MBSR groups), and the TAU (15 participants; MBSR after surgery). The individuals in the MBSR group will receive a pre-operative 8-week community-based MBSR course, which includes group classes lasting 2.5 hours a week, 45-minutes of home practice 6 days per week, a 1-hour orientation session at the beginning, and a full-day silent retreat at the end. During the orientation, participants will complete the study measures for this study. Two weeks prior to the surgery at the pre-anesthesia clinic, patients will receive another short self-reported questionnaire between the MBSR intervention and TAU groups. Patients will subsequently receive post-operative questionnaires at the following regularly scheduled post-operative appointments: 6-8 weeks after surgery, and at 6 month and 1 year follow-ups. Clinic personnel, who are blinded to assignment, will administer these measures with all other regularly distributed clinical measures. Clinic personnel will also review the chart to inform researchers as to what physical condition contributed to the need for a TKA. The TAU group will have the opportunity to enroll in an MBSR course following the completion of the study (after approximately 1 year), at no cost.

Hypotheses: We predict that pre-operative MBSR will improve post-surgical outcomes including reductions in post-operative pain (pain behavior, pain catastrophizing),

improved physical functioning (pain interference, psychosocial illness impact), enhanced quality of life (global health), reduced emotional distress (anxiety and depression), enhanced cognitive skills (Cognitive Concerns), and improved sleep (fatigue, sleep disturbance) compared to TAU group.

MBSR is an empirically-supported intervention that has been used to examine various health outcomes and psychological factors in both health conditions (e.g., chronic pain; 29, anxiety and depression; 28, and binge and emotional eating; 32) and more recently, surgical populations (spontaneous subarachnoid hemorrhage surgery; 37). We are therefore confident that MBSR will improve the psychological factors and the physical health factors we described above.

(d) The Selection of Participants / Sample Size Calculations

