Statistical Analysis Plan

We will be looking at changes in outcomes from before to after the MBSR intervention in (a) the MBSR compared to TAU participants, and (b) within the MBSR participants. We will focus on within-persons mean differences using paired samples t-tests within the intervention group. To determine the impact of MBSR on the postoperative TKA outcomes, we will conduct multivariate analyses of variance of conceptually linked dependent variables (i.e. pain variables, mental health variables) with significant results followed up by Tukey post-hoc tests.

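### No primary efficacy scale or visit is named, nothing controls error across outcome families or visits, and with two arms the planned Tukey follow-up is an unadjusted t-test.

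*SAP*

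**What the plan says.** The SAP is one paragraph, identical to Protocol section 1(f). It has two parts.

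- **Within the MBSR arm:** "We will focus on within-persons mean differences using paired samples t-tests within the intervention group".
- **Between arms:** "multivariate analyses of variance of conceptually linked dependent variables (i.e. pain variables, mental health variables) with significant results followed up by Tukey post-hoc tests".

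The two families in the parenthesis are the only ones named, and their member scales are not listed.

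Protocol 1(a) describes the aim in two ways: "This study aims to pilot the effectiveness of an empirically supported intervention", and "using a superiority randomized controlled trial (RCT) design". Protocol 1(c) puts feasibility first ("The primary objectives are (a) to determine if an 8-week pre-operative MBSR program is feasible in a TKA population"). Under objective (b) it then lists ten scales in six domains. These are pain behavior and pain catastrophizing, pain interference and psychosocial illness impact, and then "enhanced quality of life (global health), reduced emotional distress (anxiety and depression), enhanced cognitive skills (Cognitive Concerns), and improved sleep (fatigue, sleep disturbance").

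Protocol 1(c) also says "Participants will be divided into two groups" (30 MBSR, taught as two classes, and 15 TAU). It schedules post-operative questionnaires at "6-8 weeks after surgery, and at 6 month and 1 year follow-ups", after one given two weeks before surgery. Protocol 1(d) calls TAU the third group and gives d = 0.8 with 2:1 allocation, but ties that effect to no scale or visit.

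Neither document states a significance level, sidedness, test order or multiplicity rule. Neither says whether visits are tested separately or together.

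**The concern.** A trial presented as a superiority RCT should let a reader tell in advance which result would count as showing superiority. Here any named family, at any of three visits, could supply it. The one follow-up procedure that sounds like a multiplicity adjustment is Tukey's, but Tukey adjusts over pairs of factor levels. With two arms there is one pair, so there is nothing to adjust. It does not address the multiplicity this plan does have, which is over scales, families and visits.

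The SAP also makes paired t-tests within the MBSR arm a focus. After surgery, change from baseline includes the effect of the knee replacement itself. A significant paired test could then be read as an MBSR benefit when TAU patients may have changed just as much.

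At stake is whether a reader of the results can separate a planned finding from a selected one.

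**Working it through.** **Inputs from the documents.** 30 v 15 patients; d = 0.8; up to 20% attrition in the MBSR arm (Protocol 1(d)); ten scales and three post-operative visits (Protocol 1(c)); two named families (SAP).

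**Assumptions, because the documents give no value.** 0.05 per test; correlation 0.3-0.6 between scales and 0.5-0.7 between visits; family membership. Three memberships were tried:
- A: pain behavior and catastrophizing; anxiety and depression.
- B: A with pain interference added to pain.
- C: B with psychosocial illness impact and cognitive concerns added to mental health.

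**1. The plan's own sample size.** For 2:1 allocation, n(TAU) = 1.5 × (z_α + z_β)² / d².
- One-sided 0.05, 80% power: 1.5 × (1.645 + 0.842)² / 0.64 = 14.5, so 15 + 30 = 45. This reproduces the stated total.
- Two-sided 0.05, 80% power: 1.5 × (1.960 + 0.842)² / 0.64 = 18.4, so 19 + 38 = 57 (60 by exact t).

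So 45 fits one single t-test at an unstated one-sided 5% level, with no allowance for attrition or multiplicity.

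**2. Tukey.** Critical t = q(0.95; k, df) / √2.

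| Factor | df | Tukey | Unadjusted t |
|---|---|---|---|
| MBSR, TAU (k = 2) | 43 | 2.017 | 2.017 |
| Two MBSR classes, TAU (k = 3) | 42 | 2.429 | 2.018 |

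With three levels Tukey adjusts over pairs of groups. If visit were a factor it could adjust over visits. The SAP states neither, and neither would adjust over scales or families.

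**3. False positives over families and visits.** As a bound under independence, two families give 1 − 0.95² = 9.8%, and two families at three visits give 1 − 0.95⁶ = 26.5%. With the assumed correlations, by simulation of Hotelling's T² for 30 v 15 under no true difference (pooled means the average of the three visits):

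| Event | Visits pooled | Per visit |
|---|---|---|
| At least one significant MANOVA, either direction | about 9-10% | about 19-24% |
| Significant MANOVA plus a significant follow-up favouring MBSR | about 3-5% | about 7-11% |

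The reference for the first row is 5%, and for the second row 2.5%, which is one direction of a single two-sided 5% test. In the second row the ratio is 3/2.5 to 5/2.5, or about 1.2-2 times, pooled. Per visit it is 7/2.5 to 11/2.5, or about 3-4 times. The three memberships differed little.

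**4. What the MANOVA gate does.** Within a two-scale family with both scales null (correlation 0.5), a gate followed by any significant follow-up occurs in about 4%. If one pain scale truly differs by d = 0.8, a false claim on another pain scale stays under 5% in a two-scale family but is 8-9% in a three-scale family. The gate therefore helps within a family at one analysis, and not across families or visits.

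**5. Power of one named test.** Noncentrality is 0.8 × √(30 × 15 / 45) = 2.53 on 43 df. Power is 0.70 two-sided or 0.80 one-sided. With 24 v 15 (20% lost from MBSR) it is 0.66 or 0.77.

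**6. First step of Holm (equal to Bonferroni), two-sided, d = 0.8, 30 v 15.** Ten scales at one visit: 0.05/10 = 0.005, power 35%. Ten scales at three visits: 0.05/30 = 0.00167, power 22%.

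**The case against.** **It is a pilot.** Protocol 1(a) and 1(d) say so, feasibility is objective (a), and only 45 patients are planned. Formal multiplicity control in such a study is partly a matter of preference. This stands, and it is why labelling the tests exploratory is a sufficient remedy. It does not dispose of the point, because 1(a) also claims a superiority design and 1(c) predicts benefit on every scale.

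**MANOVA already protects.** It does so in part, within one family at one analysis (step 4).

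**Tukey might adjust something.** It would if the classes were separate levels or if visit were a factor. The SAP says neither, so the fair statement is that the handling of visits is unspecified.

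**The error rates are easily overstated.** This is correct, and three stronger readings should be resisted.
- A reader might take 9-10% or 19-24% as the chance of falsely declaring MBSR superior. Those are MANOVA rejections in either direction. A false claim in favour of MBSR is rarer, and under pooling it is no more than about 5%.
- A reader might count all six domains at every visit and arrive at roughly 41-52%. The SAP names two families and does not say that each visit is tested separately.
- A reader might attach a large false-positive rate to the paired t-tests. That would assume no true change after surgery, which is implausible. It would also assume that all ten scales are given at every visit, and the protocol does not itemise the post-operative questionnaires. A significant paired change may well be real. The fault is the missing comparator, which no type I error percentage measures.

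**Conclusion.** The point holds as a fault in the analysis plan that should be corrected. Three parts follow from the text alone: no primary efficacy scale or visit is named; nothing controls error across families or visits; and with the two arms that the SAP compares, Tukey is the unadjusted t-test. The paired t-tests within MBSR cannot show benefit over TAU whatever their p-values. Even the pre-surgical change, which is free of the surgical effect, is compared with nothing.

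The size is moderate. A false claim favouring MBSR rises from 2.5% to about 3-5% if visits are pooled, or 7-11% if each is tested. These ranges rest on an assumed 0.05 level, the two named families with assumed members, and the assumed correlations. The documents do not support saying that the trial is likely to report a false superiority result. They support saying that a reader could not tell which result had been meant to decide the question.

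**What to change.** State that the analysis factor is MBSR (30, both classes pooled) v TAU (15), give the significance level and sidedness, and delete the Tukey step. Then choose one of the following.

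1. **Exploratory, which fits the pilot and feasibility aim.** Declare all between-arm efficacy tests exploratory, report estimates with 95% confidence intervals, and make no superiority claim.
2. **Single primary, if a superiority claim is wanted.** Name one scale and one visit, tested once. Report everything else with estimates and 95% intervals, and use Holm-adjusted p-values for any further claim.

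Under either option, label the paired t-tests within MBSR as descriptive. If MANOVA is kept, list the scales in each family, including where global health, fatigue and sleep disturbance belong, and say how visits enter.

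**Cost.** No added patients or visits. Option 1 gives up a superiority claim. Option 2 accepts the single-test power in step 5 of the working, which is below 80% two-sided even before attrition, and leaves little prospect of a Holm-adjusted claim on other scales (step 6).
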